6.1.1. Administration

For fasted periods:

- Following an overnight fast of at least 10 hours, participants will receive study intervention at approximately 08:00 hours (plus or minus 2 hours) without breakfast on Day 1.

For fed period(s):

- Following an overnight fast of at least 10 hours, participants will receive breakfast approximately 30 minutes prior to dosing on Day 1 which is to be completed within approximately 20 minutes as outlined in [Section 5.3.2](#). The participants will then receive study intervention approximately 10 minutes after completion of the meal at approximately 08:00 hours (plus or minus 2 hours).

For all periods, investigator site personnel will administer a single oral dose of study intervention on Day 1 of each period with ambient temperature water to a total volume of approximately 240 mL. Study intervention will be administered according to the EDR.

Administration of study intervention(s) will be performed by an appropriately qualified and trained member of the study staff as allowed by local, state, and institutional guidance.

Following administration of study intervention(s) at the site, participants will be observed for up to 2 hours post-dose by an appropriately qualified and trained member of the study staff. Appropriate medication and other supportive measures for management of a medical emergency will be available in accordance with local guidelines and institutional guidelines.

6.2. Preparation, Handling, Storage, and Accountability

1. The investigator or designee must confirm that appropriate conditions (eg, temperature) have been maintained during transit for all study interventions received and any discrepancies are reported and resolved before use of the study intervention.
2. Only participants enrolled in the study may receive study intervention and only authorized site staff may supply, prepare, and/or administer study intervention.
3. All study interventions must be stored in a secure, environmentally controlled, and monitored (manual or automated recording) area in accordance with the labeled storage conditions with access limited to the investigator and authorized site staff. At a minimum, daily minimum and maximum temperatures for all site storage locations must be documented and available upon request. Data for nonworking days must indicate the minimum and maximum temperatures since previously documented upon return to business.
4. Any excursions from the study intervention label storage conditions should be reported to Pfizer upon discovery along with actions taken. The site should actively pursue options for returning the study intervention to the labeled storage conditions, as soon as possible. Once an excursion is identified, the study intervention must be quarantined and not used until Pfizer provides permission to use the study intervention. Specific details regarding the excursion definition and information to report for each excursion will be provided to the site in the CRU site procedures.
5. Any storage conditions stated in the SRSD will be superseded by the storage conditions stated on the label.
6. Study interventions should be stored in their original containers.
7. The investigator, institution, head of the medical institution (where applicable), or authorized site staff is responsible for study intervention accountability, reconciliation, and record maintenance (ie, receipt, reconciliation, and final disposition records), such as the IPAL or sponsor-approved equivalent. All study

interventions will be accounted for using a study intervention accountability form/record.

8. Further guidance and information for the final disposition of unused study interventions are provided in the CRU site procedures. All destruction must be adequately documented. If destruction is authorized to take place at the investigator site, the investigator must ensure that the materials are destroyed in compliance with applicable environmental regulations, institutional policy, and any special instructions provided by Pfizer.

Upon identification of a product complaint, notify the sponsor within 1 business day of discovery.

6.2.1. Preparation and Dispensing

Within this protocol, preparation refers to the investigator site activities performed to make the study intervention ready for administration or dispensing to the participant by qualified staff. Dispensing is defined as the provision of study intervention, concomitant treatments, and accompanying information by qualified staff member(s) to a healthcare provider, participant, in accordance with this protocol. Local health authority regulations or investigator site guidelines may use alternative terms for these activities.

PF-07853578 and placebo oral dosing solutions/suspensions will be prepared in the CRU by 2 operators, 1 of whom is a pharmacist. Details of dose preparation will be given in a separate EDR. Prepared doses will be provided in unit dose containers and labeled in accordance with Pfizer regulations and the investigator site's labeling requirements.

PF-07853578 and placebo will be prepared by qualified unblinded site personnel according to the IPM. Blinded study intervention will be administered in a blinded fashion to the participant.

6.3. Assignment to Study Intervention

The investigator will assign participant numbers to the participants as they are screened for the study. Pfizer will provide a randomization schedule to the investigator and, in accordance with the randomization numbers, the participant will receive the study treatment regimen assigned to the corresponding randomization number.

6.4. Blinding

This is a double-blind (sponsor-unblinded) study.

6.4.1. Blinding of Participants

Participants will be blinded to their assigned study intervention.

6.4.2. Blinding of Site Personnel

Investigators and other site staff will be blinded to participants' assigned study intervention.

Participants will be assigned to receive study intervention according to the assigned treatment group from the randomization scheme. Investigators will remain blinded to each participant's assigned study intervention throughout the course of the study.

In order to maintain this blind, an otherwise uninvolved third party will be responsible for the preparation and dispensing of all study intervention and will endeavor to ensure that there are no differences in time taken to dispense or visual presentation, following randomization or dispensing. This third party will instruct the participant to avoid discussing the taste, dosing frequency, or packaging of the study intervention with the investigator.

In the event of a quality assurance audit, the auditor(s) will be allowed access to unblinded study intervention records at the site(s) to verify that randomization/dispensing has been done accurately.

PCRU pharmacy staff responsible for preparing all study interventions will be unblinded. PCRU site staff providing technical system support to pharmacy staff and supporting blinded laboratory data processes will be unblinded. These site staff providing system support will not be involved in any data collection or clinic floor activities.

6.4.3. Blinding of the Sponsor

As this is a sponsor-open study, the sponsor may conduct unblinded reviews of the data during the course of the study for the purpose of safety assessment, facilitating dose-escalation decisions, facilitating PK/PD modeling, and/or supporting clinical development. Unblinded results will be reviewed by a designated limited number of sponsor colleagues within the study team.

6.4.4. Sensitive Clinical Data

Sensitive clinical data are data collected in this study that have the potential to unblind a participant's treatment assignment. Access to sensitive clinical data will be restricted to authorized individuals until the study has been unblinded. The following data variables are considered sensitive clinical data:

- Study intervention assignments (PF-07853578 or placebo);
- PK data.

6.4.5. Breaking the Blind

The method for breaking the blind in this study will be manual. In case of an emergency, the investigator has the sole responsibility for determining if unblinding of a participant's treatment assignment is warranted. Participant safety must always be the first consideration in making such a determination. If the investigator decides that unblinding is warranted, the investigator should make every effort to contact the study medical monitor prior to

unblinding a participant's treatment assignment unless this could delay further management of the participant. If a participant's treatment assignment is unblinded, the sponsor must be notified within 24 hours after breaking the blind. When the blinding code is broken, the reason must be fully documented and entered on the CRF.

Blood specimens will be obtained from all participants for PK analysis to maintain the study blind at the investigator site. Only the investigator site staff and blinded study monitor, if assigned, will be blinded to study treatment. Other Pfizer personnel will be unblinded to participant treatments in order to permit real-time interpretation of the safety and PK data; and provide information necessary to potentially alter the dose-escalation sequence. The blinded study monitor, if assigned, will remain blinded to treatment until all monitoring for the study has been completed. Specimens from participants randomized to placebo will not be routinely analyzed. To minimize the potential for bias, treatment randomization information will be kept confidential by Pfizer unblinded personnel and will not be released to the blinded investigator or blinded investigator site personnel until the study database has been locked or the investigator requests unblinding for safety reasons.

6.5. Study Intervention Compliance

When the individual dose for a participant is prepared from a bulk supply, the preparation of the dose will be confirmed by a second qualified member of the study site staff.

When participants are dosed at the site, they will receive study intervention directly from the investigator or designee, under medical supervision. The date and time of each dose administered in the clinic will be recorded in the source documents and recorded in the CRF. The dose of study intervention and study participant identification will be confirmed at the time of dosing by a member of the study site staff other than the person administering the study intervention. Study site personnel will ensure that the study intervention was ingested.

6.6. Dose Modification

The decision to proceed to the next dose level of PF-07853578 (either an increase, decrease, or repeat of a previous dose level) will be made by the study team and the investigator based on safety, tolerability, and preliminary PK data obtained at the prior dose level. At least 6 participants (including at least 1 placebo participant) must complete the prior dose level. PK data through at least 24 hours post-dose and safety and tolerability data through at least 48 hours post-dose of the current period will be reviewed. Cumulative safety and tolerability from all previous periods will also be reviewed.

The dosing schedule may also be adjusted to expand a dosing cohort to further evaluate safety, tolerability, and/or PK findings at a given dose level or to add cohorts to evaluate additional dose levels or repeat dose levels. The study procedures for these additional participant(s)/cohort(s) will be the same as that described for other study participants/cohorts.

Precautionary sentinel dosing will be used in this study. Two participants (1 receiving PF-07853578 and 1 receiving placebo) within a period will be dosed initially before the remaining participants of that period are dosed. Safety and tolerability data through at least 24 hours post-dose for the sentinel participants will be reviewed prior to dosing the

PFIZER CONFIDENTIAL

CT02-GSOP Clinical Pharmacology Protocol Template (14 April 2023)

Page 43

remaining participants of that period. Sentinel dosing may be omitted when repeating a dose level or administering a lower dose level than previously evaluated.

6.6.1. Dose Escalation and Stopping Rules

Dose escalation stopping rules will be used to determine whether the maximal tolerated dose has been attained. Dose escalation may be stopped if it is determined that the limits of safety and/or tolerability have been reached. This decision will be made after a discussion takes place between the sponsor study team and the investigator. The sponsor study team may not overrule the investigator's decision to stop dose escalation. If dose escalation is stopped because of any of these criteria, additional cohorts may receive the same or lower doses of the study intervention.

The dose escalation will be terminated based on the following criteria:

- If 50% or more of the participants receiving active drug at a given dose level (but not participants receiving placebo) develop similar clinically significant laboratory, ECG, or vital sign abnormalities, in the same organ class, indicating dose-limiting intolerance.
- Severe nonserious AEs, considered as, at least, possibly related to study intervention administration, in 2 participants at a given dose level (but not participants receiving placebo), independent of within or not within the same system organ class, indicating dose-limiting intolerance.
- Dosing will be paused for any SAE that occurs in a participant receiving active treatment until causality is fully assessed by the PI and sponsor. Dosing may resume if the SAE is determined to be not drug-related by the PI and sponsor. If the SAE is determined to be either drug-related or unknown, either dosing will cease or the SAE will be evaluated by the sponsor's protocol review committee (or similar review group), which is independent of the study team and investigators. If the protocol review committee determines that dosing may resume, a plan that mitigates risks to participants with the resumption of dosing will be implemented. Such a plan could include a revision of inclusion/exclusion criteria, repeating or reducing the dose, or adding appropriate safety monitoring.
- It is determined that the limit of safety and/or tolerability has been reached. This decision will be made following discussions between the study team and the investigator.
- Other findings that, at the discretion of the study team and investigator, indicate that dose escalation should be halted.
- If, at any dose level, the average exposure reaches or exceeds the PK stopping limits:
CCI [REDACTED]

- If, based on the observed data, the group mean C_{max} or AUC (based on total plasma concentration) of the next planned dose is projected to exceed the escalation limits, that dose will not be explored. Modified doses may be explored if they are not expected to exceed PK stopping criteria.

Progression to the next dose will occur if the last dose was well tolerated and after satisfactory review of the available safety and PK data.

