Screening activities will be completed over the 28 days prior to randomization in Period 1. In each period, participants will be admitted to the CRU on Day -1 and will remain in the CRU through at least the 72-hour assessments on Day 4. Participants may remain in the CRU after completion of Day 4 activities at the discretion of the investigator or if safety, tolerability, or PK data dictate the need to prolong confinement in the CRU. Participants will receive a single oral dose of PF-07853578 or placebo on Day 1 of each period. Dose levels will be escalated to bracket the expected clinical dose range, but the projected exposures will not exceed the predefined human exposure limits. Within an individual participant, there will be a washout interval of at least 10 days between doses. The total duration of participation from the screening visit to the telephone follow-up contact will be approximately 17 weeks for each participant. Participants will return for an on-site follow-up visit 7-10 days after the final dose of study intervention. The follow-up contact may occur via telephone contact and must occur 28-35 days after administration of the final dose of study intervention.

Dosing will occur in the fasted state for all periods, except if an optional exploratory assessment of the effect of food on PF-07853578 PK is conducted. If the food effect is evaluated, it is anticipated that study intervention will be administered in the fed state in the last period of Cohort 2 or Cohort 3 at a dose level that was previously administered fasted within the same cohort. However, study intervention may be administered in the fed state during any of the study periods/cohorts if thought necessary to achieve study objectives. The actual dose level will be selected based on emerging safety, tolerability, and PK data but will be expected to achieve approximate projected therapeutic exposures ([Section 4.3.2](#)).

If evaluated, the IDS oral solution of PF-07853578 is anticipated to be assessed in the last period of Cohort 2 or Cohort 3 at a dose level that was previously administered as a suspension within the same cohort. However, the IDS oral solution may be administered during any of the study periods/cohorts if thought necessary to achieve study objectives.

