4.2. Scientific Rationale for Study Design

The purpose of this study is to evaluate the safety, tolerability, and PK of orally administered doses of PF-07853578 and placebo in healthy adult males and female participants of non-childbearing potential. Female participants will be confirmed not to be of childbearing potential **CCI**

[REDACTED], and reproductive toxicity studies with PF-07853578 have not been conducted. In male participants, appropriate measures are expected to be followed to minimize potential transfer of PF-07853578 via semen to partners (see [Appendix 4](#)).

Because this is the first time PF-07853578 will be administered to humans, an escalating single, oral dose, crossover interleaving design is planned with careful assessment and ongoing review of safety, tolerability, and PK data of PF-07853578. In each period, 6 participants are planned to receive PF-07853578, and 2 participants are planned to receive placebo. Sentinel dosing will be utilized to ensure that safety and tolerability data in a subset of 2 participants at each dose level supports the testing of additional participants. The crossover design permits both within- and between-participants assessments of safety, tolerability, and PK at multiple dose levels and placebo.

The highest anticipated C_{max} and AUC_{24} of PF-07853578 will not exceed the pre-defined human exposure stopping limits. Furthermore, to permit an unbiased assessment of safety, the administration of both PF-07853578 and placebo in each period will be blind to both site staff (except those involved in preparation of doses) as well as the participants. To permit real-time review of the safety, tolerability, and PK data, a limited number of sponsor study team members will be unblinded.

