The actual dose levels, target exposures, and/or dose level increments may be adjusted (higher or lower) during the study based on emerging human safety, tolerability, and PK data, but projected exposures will not exceed the predefined human exposure limits. Dose levels may also be repeated if warranted.

When the assessment of the effect of food on the PK of PF-07853578 is conducted, the dose level will be selected based on emerging safety, tolerability, and PK data from previous periods of this study. The actual dose level used will be expected to achieve exposures similar to or greater than projected therapeutic exposures (as outlined in [Section 4.3.2](#)).

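### Section 6.6.1 allows a dose to be given again after a PK stop without saying whether the cap on projected exposure still applies

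*Protocol*

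**What the plan says.** The opening paragraph of Protocol Section 6.6.1 gives one general instruction for dosing after escalation has stopped: "If dose escalation is stopped because of any of these criteria, additional cohorts may receive the same or lower doses of the study intervention". The bulleted list of criteria follows. One bullet is the PK criterion: "If, at any dose level, the average exposure reaches or exceeds the PK stopping limits". The numerical limits after it are redacted.

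The next bullet looks forward. If the group mean Cmax or AUC "of the next planned dose is projected to exceed the escalation limits, that dose will not be explored". It allows modified doses only where they are not expected to exceed the PK criteria.

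Three other sections state the exposure commitment:

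- Section 4.1 says doses will be escalated, "but the projected exposures will not exceed the predefined human exposure limits". SAP Section 2.3 repeats this.
- Section 4.2 says the highest anticipated Cmax and AUC24 "will not exceed the pre-defined human exposure stopping limits".
- Section 4.3.4 lets dose levels be adjusted, "but projected exposures will not exceed the predefined human exposure limits. Dose levels may also be repeated if warranted".

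Section 6.6 treats the decision on the next dose level as one that may go up, go down or return to a level already given.

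**The concern.** The permission in the opening paragraph of 6.6.1 covers every criterion in the list, and the PK criterion is one of them. Read literally, a dose whose observed mean is above the limit may be given to a further cohort, while a dose that is merely projected to be above the limit may not be given at all.

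The exposure limit is the plan's numerical boundary for a first-in-human study in healthy volunteers. If the two instructions are not reconciled, a team could follow 6.6.1 and still give a dose whose projected exposure breaks the commitments elsewhere. Sections 4.1 and 6.6 also allow sentinel dosing to be left out when a dose level is repeated, and they do not refer to the limits. So the case that most needs one clear rule is left to interpretation.

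**Working it through.** The plan gives no figure to reproduce: there is no hypothesis test (Section 9.1), and the limits are redacted. The check sets the passages side by side.

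**Notation.** L is the PK stopping limit. M is the observed group mean at a dose. P is the projected group mean if that dose is given again.

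**Step 1: reach of the permission.** The sentence refers to criteria in the plural and to any of them. The sentences before it name only one ground, reaching the limits of safety or tolerability. The natural referent is the bulleted list below, which includes the PK bullet. The reference comes before the list, so some doubt remains.

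**Step 2: trigger.** The PK bullet fires when M ≥ L.

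**Step 3: projection for a repeat.** With the same fasting state and formulation, and nothing else to inform the projection, P = M. With a different fasting state or formulation, P may differ from M. Section 4.2 itself expects that food may raise exposure.

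**Step 4: compare the instructions.**

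| Case | 6.6.1 opening paragraph | Commitments in 4.1, 4.2, 4.3.4 (P must not exceed L) | 6.6.1 bullet on the next planned dose |
|---|---|---|---|
| M > L, same conditions, so P > L | Same dose permitted | Not met | Barred, if a repeat counts as a next planned dose |
| M = L, same conditions, so P = L | Same dose permitted | Met | Not barred |
| M ≥ L, different fasting state or formulation | Same dose permitted | Depends on P | Depends on P |

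The conflict is confined to the first row.

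**Step 5: does the next-planned-dose bullet settle the first row?** Not explicitly. It speaks of the next planned dose and of escalation limits, in a list of grounds for ending escalation, and giving a dose again is not escalation. Section 6.6 does count a repeat as a possible next dose level, but in another section and in different words. Combining the two can extend the bar to a repeat, but the reader has to make that combination.

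**Step 6: size.** Each period randomises 8 participants 6:2 (Sections 4.1 and 9.5), so a repeat period adds about 6 participants on active drug at the dose in question. No probability of a second exceedance is given. It would depend on an assumed between-participant variability and an assumed distance of M above L, and the documents provide neither.

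**The case against.** The best defence is that the passages can be read together. The sentence in 6.6.1 is permissive, whereas the exposure commitments and the next-planned-dose bullet are mandatory, and a general permission does not normally override a specific prohibition. Section 4.3.4 puts the cap directly before its own permission to repeat doses, which suggests that repeats were meant to fall under it. Section 6.6 requires the study team and the investigator to review safety and PK data before any next dose level. Section 6.6.1 closes by making progression depend on a satisfactory review. Any wording after the PK bullet is redacted and might bear on the point.

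Much of this stands. The harmonising reading is available and may be what the sponsor intends, which is why confidence is moderate. It does not remove the point. It works only by cancelling an express permission, and the sentence in 6.6.1 is the one general instruction on dosing after a stop, so another reader could take it as the specific rule. A review meeting also needs to know which instruction it is applying.

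The objection also correctly limits the scope. The same dose in milligrams need not mean the same exposure, because fasting state and formulation can differ between periods.

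**Conclusion.** The point holds for one case. When the observed group mean at a dose has exceeded the PK stopping limit, the same-dose permission in 6.6.1 conflicts with the commitments on projected or anticipated exposure in 4.1, 4.2 and 4.3.4. It also sits uneasily with the bar on a next planned dose projected above the limits. This rests on two assumptions: that the permission reaches the PK bullet, and that the projection for a repeat under the same conditions equals the observed mean. About 6 active-treated participants per repeat period are concerned.

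A reader might infer more, but the documents do not support it:

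- **That the plan promises no observed exposure above the limit.** The commitments concern projected or anticipated exposure, so an observed mean above the limit does not by itself breach them.
- **That merely reaching the limit creates the conflict.** The PK bullet fires on reaching it, but the commitments forbid only exceeding it.
- **That the SAE bullet is contradicted too.** Stopping dosing is one of two routes there. The other is independent committee review, and the resulting plan may expressly include giving the same dose again.
- **That a repeat after dose-limiting intolerance is forbidden elsewhere.** No passage says so.
- **That a second exceedance has a known chance of about one half or more.** That figure follows only from assuming that the true mean is at or above the limit.

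**What to change.** Reconcile the opening paragraph of 6.6.1 with its two PK bullets and with Sections 4.1, 4.2, 4.3.4 and 6.6. The text should state whether the permission to give the same dose after a stop is subject to the exposure limits, and whether the next-planned-dose bullet covers a repeat, so that one instruction governs the PK-stop case. If a change of fasting state or formulation is meant to matter, the text should say so. The content is for the sponsor to decide. The SAE and intolerance bullets need no change on this account.

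The cost is a short wording change at the next amendment. Depending on what the sponsor decides, there may be less freedom to repeat a dose after a PK stop. No analysis or sample size is affected.
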